z.r) Randomized, Efficacy Study -- Surgical Techniques/Interventions

Discuss the research design including but not limited to such issues as: probability of group assignment, potential for subject to be randomized to placebo group, use of control subjects, etc.

50% of patients will be randomized into the EU-PC and 50% into the APT intervention. It is equally likely that a participant will be randomized into either intervention. The RA will not know when consenting the subject if they will be in the active APT intervention or in the control group (EU-PC).

Inclusion Criteria:

Patients can participate in the study if they meet the following criteria: (1) have a documented diagnosis of dementia; (2) receive care from, BCM GMA, the BCM Alzheimer Center, or Kelsey-Seybold; (3) reside outside Nursing Home; (4) live within 40 miles of the Texas Medical Center; (5) have mild-to-moderate dementia; (6) have no history of aggression in the past month; (7) have an informal caregiver directly involved with them at least 8 hours a week who sees them at least twice a week; (8) speak English; and (9) report clinically significant pain, depression, or caregiver/PWD relationship difficulties (either self-report or caregiver proxy-report).

Exclusion Criteria:

Patients with advanced dementia will be excluded by 2 criteria: a) score of greater than 6 on the Functional Assessment Staging (FAST) scale; or b) inability to complete by phone the Memory Impairment Screen--Telephone Version (MIS-T) or Philadelphia Geriatric Pain Intensity Scale. PWD will also be excluded if they have been aggressive in the past month; we will administer the aggression subscale of the Cohen-Mansfield Agitation Inventory (CMAI).

F2. Procedure

Our patient identification and recruitment procedures are based on our prior studies of PWD. The key initial criterion for study eligibility for patients is having a dementia diagnosis. The research team will partner with participating sites through 3 recruitment mechanisms to identify PWD: (1) direct provider referral (2) patient self-referral and (3) partial HIPAA-waiver-approved, database-generated lists of patients meeting geographical and selected ICD-9 codes from the 046, 290, 291, 292, 294, 331 and 333 series (or corresponding ICD-10 codes).

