We plan to use the information collected on the screening telephone call as research data for the following reasons: 1) We will use the information gathered to determine the reasons potential subjects did not want to participate in the study or did not qualify for the study, to aid in the design of future research targeting this population. 2) Some of the questions asked at screening are also needed to characterize participants that enroll in the study. To reduce study burden, we will not repeat these questions after written informed consent is obtained.

Participants who screen eligible during the telephone assessment and sign consent documents will proceed to baseline. Eligible participants will be randomly assigned to intervention groups (APT or EU-PC) immediately following baseline evaluation based on random numbers generated in SAS PROC PLAN.

Assessments. Assessments will be done at baseline and 3, 6, and 12 months and will consist of a measure of demographic information and validated instruments. They will be administered by independent evaluators (IEs) blinded to random assignment. The CLOX Drawing Test (see Section S) will be administered in-person at baseline to a subset of 100 consecutively enrolled subjects; it should take less than ten minutes to complete. Prior to the assessment, instructions will be given to each subject in terms of what the measure is testing (i.e. ¿I will be assessing your ability to draw a clock¿). The remainder of the assessments will be administered by telephone. An unblinded RA will notify the PCP or referring MD of patients who have been identified as having clinically significant pain, depression, or aggression at baseline or on any of the follow-up calls (see Documentation and Reporting Guidelines attached in Section S).

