In general, the primary source of missing data will be through participant attrition. We anticipate a low attrition rate (10%) based on our prior work. As described below, we will use analytic techniques (eg, hierarchical linear models) that are robust to violation of missing-data assumptions (ie, ¿missing completely at random¿). To reduce the possibility of bias in missing data, where possible, we will incorporate information from secondary sources for participants with missing data from attrition to try to ascertain whether they differ in important ways from other study participants. We will use X2 tests to determine whether there are differences in attrition between the 2 study arms. Prior to testing hypotheses, we will compare baseline demographic and clinical variables in APT and EU-PC with X2 and independent sample t-tests. Variables with p values < .25 in these univariate tests will be included as covariates in all subsequent multivariate models107 or as propensity scores.

Primary Hypothesis: APT will result in lower 1-year incidence of aggression than EU-PC. We will use negative binomial regression models to estimate the difference between our intervention and the control group in the rate of aggressive behavior at the 1-year follow-up period. For participants who drop out of the study, their time until study attrition will be used as their exposure period. Statistical significance will be determined using the X2 statistic associated with the parameter estimate for group membership. Baseline demographic and clinical variables that differ between groups in univariate tests will be included as covariates or propensity scores.

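### The primary endpoint is 1-year incidence of aggression, but the follow-up look-back is not stated, and drop-outs' exposure includes time that no interview covers

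*Combined protocol and SAP*

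**What the plan says.** Section F2 (Assessments) states: "Assessments will be done at baseline and 3, 6, and 12 months". Blinded evaluators conduct the interviews, almost entirely by telephone. Follow-up measures are described there only as validated instruments, with no recall period for aggression.

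The primary hypothesis in Section G1 is that "APT will result in lower 1-year incidence of aggression than EU-PC". It is tested with a negative binomial model for the arm difference "in the rate of aggressive behavior at the 1-year follow-up period". For participants who drop out, "their time until study attrition will be used as their exposure period"; no exposure rule is written for completers. On drop-out, the plan says: "We anticipate a low attrition rate (10%) based on our prior work". The text under Secondary Hypotheses 1 refers back to the primary analysis as one of onset of aggression.

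A one-month window appears twice, both times in Section F1. The patient must "have no history of aggression in the past month", and "PWD will also be excluded if they have been aggressive in the past month". The aggression subscale of the Cohen-Mansfield Agitation Inventory (CMAI) is named only there, as the tool for that exclusion.

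The other scheduled contacts are 6 to 8 weekly APT sessions, 8 weekly EU-PC calls and an exit interview for APT caregivers about the intervention. Aggression noticed in sessions or calls is reported to the physician, but Section G1 (Data on Intervention Process and Quality Assurance) keeps study providers out of outcome collection.

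**The concern.** An incidence over a year needs every part of the year to be asked about. The interviews are 3, 3 and 6 months apart, and the text reviewed does not say that they reach back over those gaps. No other contact supplies outcome data. An episode that begins and resolves between two recall windows would leave no trace in the primary outcome. The longest gap lies between the 6- and 12-month calls, when a fading treatment effect would show.

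Two things are at stake. The first is whether the reported figure is a 1-year incidence or the prevalence of recent aggression at three time points. The second is whether the denominator of the rate matches the time over which aggression could be recorded.

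**Working it through.** The plan gives no event rate, effect size, power or observed time for the aggression endpoint, so there is no figure of its own to reproduce. The look-back w is an assumption, shown over a range.

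**1. Time covered for a completer.** Interviews are at 3, 6 and 12 months (Section F2), so the intervals are 3, 3 and 6 months. Covered time = min(w,3) + min(w,3) + min(w,6).

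| Look-back w | Months covered | Share of 12 |
|---|---|---|
| 1 week | 0.69 | 6% |
| 2 weeks | 1.38 | 12% |
| 4 weeks | 2.77 | 23% |
| 1 month (the eligibility window) | 3 | 25% |
| 2 months | 6 | 50% |
| 3 months | 9 | 75% |
| Since last interview | 12 | 100% |

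**2. Episodes missed if w = 1 month.** The windows are months 2–3, 5–6 and 11–12, which leaves gaps of 2, 2 and 5 months. An episode of length d is missed if it starts and ends inside one gap. With onsets uniform over 12 months:

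share missed = [2 × max(0, 2 − d) + max(0, 5 − d)] / 12

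| d (months) | Calculation | Missed |
|---|---|---|
| 0 (momentary act) | (4 + 5)/12 | 75% |
| 1 | (2 + 4)/12 | 50% |
| 2 | (0 + 3)/12 | 25% |
| 3 | (0 + 2)/12 | 17% |
| 4 | (0 + 1)/12 | 8% |
| 5 or more | 0/12 | 0% |

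**3. Effect on the comparison.** Observed incidence = true incidence × detection share. With the same episode length in both arms, the detection share cancels in the ratio. If lengths differ, it does not. As an illustration, take equal true onset in both arms and three-month episodes under EU-PC (detection 1 − 2/12 = 0.83):

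- one-month episodes under APT: 0.50/0.83 = 0.60;
- two-month episodes under APT: 0.75/0.83 = 0.90.

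Either ratio would arise with no aggression prevented.

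**4. Exposure for drop-outs.** Covered time divided by time to attrition:

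| Attrition at month | w = 1 month | w = since last interview |
|---|---|---|
| Before 3 | 0% | 0% |
| 3, just after the call | 1/3 = 33% | 3/3 = 100% |
| 5.9 | 1/5.9 = 17% | 3/5.9 = 51% |
| 9 | 2/9 = 22% | 6/9 = 67% |
| 11.9 | 2/11.9 = 17% | 6/11.9 = 50% |

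So the mismatch remains even with full look-back. To bound it in that case, 10% of 220 dyads is 22, each losing just under 6 months at most: 22 × 6 = 132 of 220 × 12 = 2,640 dyad-months, or 5%. If all 22 were in one arm of 110, it would be 132 of 1,320, or 10% of that arm's exposure.

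**The case against.** The strongest reply is that the past-month window belongs to eligibility. A reader might infer that the outcome is defined over the past month and that completers are therefore seen for only 3 of 12 months. The documents do not say so. The follow-up look-back is unstated, and the assessment attachments in Section S, which are not in the text reviewed, may set it. This stands: the 25% is one conditional case.

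A reader might also infer that three months of counts over twelve months of exposure understates the rate fourfold and so damages the primary test. Full-year exposure for completers is not written. If it were used, an exposure common to all completers would move only the model intercept and leave the rate ratio and its test among them unchanged. The loss is in the absolute rate and in the number of events captured.

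Nor do the documents support the inference that aggression-related injuries go uncounted. Injuries are a separate outcome with no stated look-back.

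Persistent aggression is always caught: the longest gap is five months, and the documents give no episode durations, so the 75% figure is the extreme. Anticipated attrition is only 10%. If attrition were dated at the last completed interview, the uncovered tail would vanish under a since-last-interview question, but the plan does not date it that way.

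What survives is that no outcome source in the text covers the intervals between calls, and that no rule ties exposure to the time asked about.

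**Conclusion.** The concern holds in conditional form. As written, the plan does not show that it measures the 1-year incidence it names. It would be wrong to conclude that it cannot: if follow-up asks about the whole time since the last interview, coverage for completers is complete and one sentence settles that part.

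If the one-month window is carried over, nine of twelve months go unobserved and short episodes are under-counted, to the extent shown above for evenly spread onsets. The treatment ratio is not biased by under-detection that is equal between arms. It could be biased if APT changes how long episodes last, because shortening would then be read as prevention. The 0.60 and 0.90 ratios show the mechanism; they are not estimates.

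The drop-out exposure problem does not depend on the look-back. Its effect on the comparison is small if attrition is near 10% and similar in the two arms, and grows if drop-out is unequal. It should be corrected because the endpoint is primary and the remedy is cheap.

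**What to change.** 1. At each follow-up call, keep the CMAI aggression subscale for frequency and state its look-back. Add an item, asked by the blinded evaluator, on whether any aggressive act has occurred since the last interview and, if so, the approximate month of the first.
2. Name the new item as the source for 1-year incidence and onset, with the CMAI count as supportive. State whether the primary comparison is of first onset or of event rate, since Section G1 uses both ideas.
3. In the negative binomial model, set every participant's exposure, drop-outs included, to the time that their completed interviews cover. For a since-last-interview measure with no missed calls, this is the time to the last completed interview. For a one-month count, it is one month per completed interview. State how participants with no follow-up interview, whose covered time is zero, are handled.
4. Report the past-month CMAI result as a sensitivity analysis.

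The cost is a question or two at calls already scheduled and a few lines in the analysis section. The downside is less precise recall over the six-month interval. That recall could also differ by arm, because caregivers know their allocation; the sensitivity analysis in item 4 is there for that reason. If Section S already contains such an item, items 2 to 4 still need to be written into the plan.

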Executive Function (EF) and Self-Neglect (SN): Individuals who SN often suffer from dementia, depression, and pain, all associated with ED. Additionally, SN is associated with impaired social networks and refusal of care. Prior research indicates that, when self-neglecters refuse interventions of unpaid caregivers, there is progressive decline in personal, functional and environmental domains. Secondary Aims have been added to further understand the relationship of ED with psychosocial outcomes and refusal of care. Although the APT intervention is primarily directed to the caregiver, participation of the PWD in weekly homework is critical. Better understanding the relationship of these variables will help to inform later analyses. The CLOX Drawing Test will be administered to a subset of 100 consecutively enrolled subjects at baseline. It is a two part test (CLOX 1 and CLOX 2) to measure EF and global cognition. CLOX 1 is a more direct measure of EF. CLOX 1 consists of instructing the subject to draw a clock and insert the time of 1:45 using hands and numbers in a clock. Scores range from 0 to 15. A score of 10 or below on CLOX 1 indicates executive impairment. The CLOX has high inter-rater reliability estimates (CLOX 1, Pearson, s r = 0.94, CLOX 2, Pearson, s r = 0.93; both p < 0.001). The CLOX also has a high internal consistency (Cronbach; s alpha = 0.82). After adjusting for age and education level, the Executive Interview and Mini-Mental Status Examination strongly predicted CLOX 1 scores [F (4,82) = 50.7, p < 0.001; R2 = 0.71]. Refusal of care will be measured by clinician assessment at each weekly session with the following two questions: ¿¿How many weeks did the PWD participate in weekly sessions with the therapist?¿, and ¿How many weeks did the PWD participate in assigned homework?; Responses to each question range from 0-7 and will be summed and divided by the total number of sessions the caregiver participated in to determine the PWD; s rate of engagement in the intervention.

Section D: Purpose and Objectives

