The objectives of this proposal are to assess whether this caregiver intervention, Aggression Prevention Training for Caregivers of Persons with Dementia (APT), decreases 1) incidence of aggression, 2) aggression-related outcomes(injuries, caregiver burden, nursing-home placement, caregiver burden, positive aspects of caregiving, and behavior problems), and 3) pain and pain-related features (decreased pleasant activity frequency, poor relationship quality, and depressive symptoms).

Secondary objectives are to examine the relationships between executive dysfunction (ED) and 1) pain, 2) caregiver-patient related problems, 3) depression and 4) behavior problems and the association between ED and PWD engagement in the APT intervention.

The proposed study is a randomized, controlled trial of APT, a 6-8 session, home-based intervention. We will recruit 220 community-dwelling dyads (PWD and caregiver) that will be randomized to APT or enhanced usual primary care (EU-PC). APT uses active learning tools, including didactics, role-playing, and multimedia (eg, books and DVDs). Four core modules will address the 4 main aggression risk factors identified by our team and others: a) recognizing pain, b) treating pain pharmacologically and behaviorally, c) increasing pleasant activities to decrease depression, and d) improving the quality of the dyadic relationship through enhanced dyadic communication skills. Caregivers can select 2 to 3 additional elective sessions; the needs of the dyad guide elective selection to further enhance skills related to these core topics. EU-PC provides the patient and caregiver educational materials on pain, notifies the primary care provider of clinically significant pain, depression, and aggression in the PWD (see Reporting and Documentation Procedures attached in Section S), and provides 8 weekly supportive telephone calls to caregivers. PWD and caregiver outcomes will be collected at baseline, and at 3, 6 and 12 months. The CLOX Drawing Test will be administered at baseline to a subset of 100 subjects to measure executive function. Data analysis will include both univariate descriptive statistics and inferential statistics, including regression models, repeated-measure modeling and Cox proportional hazards models.

Section E: Protocol Risks/Subjects

E1. Risk Category

Category 1: Research not involving greater than minimum risk.

E2. Subjects

Gender:

Both

Age:

Adult (18-64 yrs), Geriatric (65+ yrs)

Ethnicity:

All Ethnicities

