
Enhanced Usual Primary Care. EU-PC participants will receive feedback on their level of pain and depression, a booklet from the National Institute on Aging on memory problems, the book, Pain Management for Older Adults: A Self-help Guide, and a letter encouraging them to discuss additional treatment options with their providers. Caregivers receiving EU-PC will also receive 8 weekly 15-minute calls to query symptom severity, ascertain needs for immediate psychiatric care, and provide minimal support. If caregivers report pain or other physical or psychological symptoms in the PWD, they will be

encouraged to address them with their primary care providers.

APT and Usual Care Interventionists. A minimum of 2 RAs with a license in nursing, social work, psychology, or counseling will provide the APT intervention and EU-PC. Each RA will be assigned both APT and EU-PC patients. Treatment diffusion will be monitored by ongoing treatment integrity ratings. All providers will receive training with emphasis on providing care for PWD and their caregivers. Training will include best practices for delivering educational interventions, skills training, and behavioral activation. Providers will not be restricted based on discipline but will be expected to have a background in mental health and interest in older adults. Providers will be blind to baseline data collected during IE telephone assessments.

APT and EU-PC intervention sessions and telephone assessments at baseline, 3, 6, and 12 months will be audio-recorded without PHI for quality assurance purposes. See data analysis section for information on security of audio-recordings.

If detected during APT or EU-PC intervention sessions or during telephone assessments at baseline, 3, 6, and 12 months, clinically significant pain, aggression, and depression symptoms will be reported to the PCP or referring MD according to the Documentation and Reporting guidelines attached in Section S. If the participant's PCP is not with Baylor College of Medicine or Kelsey-Seybold, he or she will be asked to complete a Release of Information Form giving permission for us to communicate this information to the PCP.

Section G: Sample Size/Data Analysis

G1. Sample Size

How many subjects (or specimens, or charts) will be used in this study?

Local: 4250 Worldwide: 4250

Please indicate why you chose the sample size proposed:

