In our prior and currently funded grants, we recruit patients using methods similar to those described in this proposal to identify PWD with clinically significant pain. To determine the number of patients available for this study, we asked our clinical partners to provide the number of PWD, using dementia ICD-IX codes and restricting to patients within 40 miles not living in a long-term care facility. We identified 1273 patients. Based on our prior studies, an estimated 60% of patients will meet the criterion for clinically significant pain, resulting in 764 existing eligible patients; broadening inclusion criteria to include pain-related features will result in even more eligible patients. On the basis of our prior recruitment data, we predict excluding approximately 30% of patients due to severe dementia, history of aggression, or lack of eligible caregiver. Thus, we estimate that 535 will meet all selection criteria. In our current APT study, we have had a consent rate of 80-90%. To conservatively estimate, an 80% consent rate results in 428 patients.

One-hundred consecutively enrolled subjects will be asked to do the CLOX Drawing Test at baseline to achieve our secondary objectives. This will give adequate power to detect significant differences of small to medium magnitude in outcomes between those with and without executive function (ED). Given an N of 100 and an alpha of 0.05, there is 97% power to detect a medium effect (F2 = 0.15) and 80% power to detect an effect size for ED (over and above two covariates) as small as F2 = 0.08.

Expected Recruitment Efforts and Minimization of Attrition. In our current VA Study and prior studies, we were able to enroll 6-8 dyads per month. In the VA study and others that we completed with PWD and their caregivers, attrition is about 10%; therefore, we plan to recruit 220 dyads, 6 patients per month over 37 months. We expect we will need to contact approximately 300 dyads using our partial HIPPA Waiver in order to enroll 220 dyads in the study.

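### The 97% and 80% power stated at N = 100 does not apply to Secondary Hypothesis 4, whose outcome arises only in the APT arm (about 50 of the 100 CLOX participants; power about 76.5% and 50%)

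*Combined protocol and SAP*

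**What the plan says.** Section G1 (Sample Size) sets the size of the CLOX subset and its purpose: "One-hundred consecutively enrolled subjects will be asked to do the CLOX Drawing Test at baseline to achieve our secondary objectives". It then makes a general claim, "This will give adequate power to detect significant differences of small to medium magnitude in outcomes", and supports it with "Given an N of 100 and an alpha of 0.05, there is 97% power to detect a medium effect (F2 = 0.15") and with 80% power at f2 = 0.08 for ED after adjustment for two covariates. No other sample size or power is given for any ED analysis.

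Section D (Purpose and Objectives) lists the ED objectives. One of them is "the association between ED and PWD engagement in the APT intervention". The data analysis plan tests it as Secondary Hypothesis 4, by a linear regression of engagement on ED. That paragraph names neither covariates nor an analysis set.

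Section C (Executive Function and Self-Neglect) defines engagement from two clinician-rated items. One concerns PWD participation in weekly sessions with the therapist; the other is "How many weeks did the PWD participate in assigned homework". Their sum is divided by the number of sessions the caregiver took part in.

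On allocation, Section F1 states "50% of patients will be randomized into the EU-PC and 50% into the APT intervention", and Section F2 states "Eligible participants will be randomly assigned to intervention groups (APT or EU-PC) immediately following baseline evaluation". On the control arm, Section F2 states "Caregivers receiving EU-PC will also receive 8 weekly 15-minute calls to query symptom severity". The rest of EU-PC is feedback, printed material and a letter.

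**The concern.** The power statement is offered for all the ED objectives, but the outcome of one of them cannot be observed in half of the CLOX subset. EU-PC, as described, has no sessions for the PWD to join and no homework. Scoring EU-PC participants as zero would not restore N = 100, because those zeros would reflect allocation and not refusal of care.

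What is at stake is how Hypothesis 4 will be read. Taken at face value, Section G1 lets a null finding be reported as coming from a test with 80% to 97% power. If the usable number is about 50, the test misses an effect of f2 = 0.08 about as often as it finds it.

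**Working it through.** **Inputs**

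- N = 100, alpha = 0.05, f2 = 0.15 and 0.08, ED tested over two covariates: Section G1.
- CLOX given at baseline to 100 consecutive enrolees, randomisation after baseline: Section F2. Allocation 50:50: Section F1. Expected number in APT: 100 × 0.5 = 50.
- Attrition of 10%, used only as a sensitivity check: data analysis plan, paragraphs on missing data.

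**Formula.** Test of one regression coefficient with two covariates: F with 1 and N − 4 degrees of freedom, and noncentrality λ = f2 × N. Power is the probability that a noncentral F with that λ exceeds the central F critical value at alpha = 0.05.

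**Step 1. Reproduce the plan's figures at N = 100** (df 1, 96).

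- f2 = 0.15: λ = 15, power 96.95% (stated 97%).
- f2 = 0.08: λ = 8, power 79.96% (stated 80%).

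Both match. A one-sided test (98.6% and 87.8%) and a 3-df overall test (90.5% and 63.4%) do not, so the plan's method is the 1-df test of ED.

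**Step 2. Same calculation at the expected N = 50** (df 1, 46).

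- f2 = 0.15: λ = 7.5, power 76.5%.
- f2 = 0.08: λ = 4, power 49.9%.

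**Step 3. Vary the number in APT.** The plan does not balance the CLOX subset by arm. Under simple 1:1 randomisation (an assumption) the APT count is Binomial(100, 0.5) and lies between 40 and 60 with probability 0.965.

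| APT participants with CLOX | Power, f2 = 0.15 | Power, f2 = 0.08 | Smallest f2 with 80% power |
|---|---|---|---|
| 40 | 66.4% | 41.3% | 0.207 |
| 45 (50 less 10%) | 71.8% | 45.7% | 0.183 |
| 50 | 76.5% | 49.9% | 0.164 |
| 60 | 83.8% | 57.7% | 0.135 |
| 100 | 97.0% | 80.0% | 0.080 |

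Averaged over the binomial distribution, power is 76.1% and 49.8%.

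**Step 4. Covariates.** None are named for Hypothesis 4. Without any (df 1, 48), N = 50 gives 76.5% and 50.0%, a change of less than 0.1 point.

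**Step 5. Number needed for 80% power.** At f2 = 0.15, 55 APT participants with CLOX (54 gives 79.7%). At f2 = 0.08, about 100 (100 gives 79.96%, 101 passes 80%).

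**The case against.** The best counter-argument is that the sentence was never meant for Hypothesis 4. It speaks of ED over two covariates, and only the Hypothesis 3 models have exactly two named. On that reading the plan contains no wrong figure; it simply gives no power for Hypothesis 4. The covariate wording is fair evidence of where the calculation came from. It does not settle its scope, because the paragraph opens by tying the 100 participants to the secondary objectives as a whole, and Section D counts engagement in APT among them. Under either reading the reader is left with no valid power for Hypothesis 4.

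A second point is that the restriction to APT is inferred. The Hypothesis 4 paragraph does not name an arm, and Section F2 in places refers to intervention sessions in both arms. That is true, but the objective names APT, and EU-PC as described has only calls to the caregiver.

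Three smaller points stand as qualifications:

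- The 40 to 60 range needs simple randomisation. Blocking is neither stated nor excluded and would hold the split nearer 50; a count of 48 to 52 gives about 75% to 78% and 48% to 52%.
- The plan gives no time point for the Hypothesis 3 outcomes, so N = 100 holds there only if all 100 complete CLOX and supply those outcomes.
- This is one non-randomised secondary association, and at the medium effect the shortfall from 80% is only 3.5 points (80 − 76.5).

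**Conclusion.** The concern holds. The stated power is arithmetically right for 100 participants and is suitable for Hypothesis 3, given complete data. For Hypothesis 4 the expected power falls from 97% to about 76.5% at f2 = 0.15 and from 80% to about 50% at f2 = 0.08. The claim that the subset is adequate for effects below medium size is not supported for this hypothesis, since even the medium effect falls short of 80%.

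This rests on two things: that engagement can be measured only in APT, which follows from its definition and the description of EU-PC, and that 1:1 allocation puts about half of the CLOX subset in APT. Neither the number of covariates nor a plausible imbalance changes the conclusion at f2 = 0.08. At f2 = 0.15, 80% would be reached only if chance placed 55 or more of the 100 in APT with no loss. The primary hypothesis and the other randomised comparisons are unaffected, so this is a correction that should be made but not one that threatens the trial.

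**What to change.** In Section G1, limit the N = 100 figures to Secondary Hypothesis 3 and add text such as:

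> Secondary Hypothesis 4 is analysed in CLOX participants randomised to APT (expected about 50 of 100). Expected power is about 76.5% at f2 = 0.15 and 50% at f2 = 0.08. If the number in APT is 40 to 60, the range expected under simple randomisation, power is 66–84% and 41–58%. With 50 participants, 80% power is reached only for f2 of about 0.16 or more, before any loss to follow-up.

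In the Secondary Hypothesis 4 paragraph, state that the model uses APT participants only and name its covariates, if any.

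The cost is wording only, together with a less favourable stated power. Labelling Hypothesis 4 exploratory with no power claim would be an acceptable alternative. Restoring 80% power at f2 = 0.08 would instead need about 100 APT participants with CLOX, hence about 200 tested (100 ÷ 0.5) of the planned 220. That is a real increase in assessment work, and it may no longer be possible given how far recruitment had gone by the latest amendment recorded in Section G1.
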